Historically, the routine diagnosis of AA has relied upon clinical observation and histopathological findings of a peribulbar infiltrate around the hair follicle, both of which are inherently subjective, non-quantitative and lack sufficient resolution to identify molecular subtypes of disease. Serum biomarkers (Benoit, S.J *Invest Dermatol* 121:933-935. Gregoriou, S., *Mediators Inflamm* 2010:928030. Kuwano, Y., 2007. *Br J Dermatol* 157:466-473. Barahmani, N., 2009. *Clin Exp Dermatol*) and scalp skin gene expression (Subramanya, R.D. 2010. *Genomics* 96:146-153. Ghoreishi, *Br J Dermatol* 163:57-62) have been studied in small series of patients (n=10 patients), and only one study from whole blood [n=9 patients (Coda, A.B., 2010. *Genes Immun* 11:531-541)] has been published, many of which have been underpowered for statistical significance. **Quantitative biomarkers for AA are a crucial addition to clinical trials in AA.** Drs. [name] and [name] have developed a biomarker instrument that can be deployed in clinical trials or monitoring of AA patients over time. This innovative approach will allow us to robustly and quantitatively assess the disease status of AA patients and set the stage for wider validation of these markers in larger AA populations in the future. **As part of this study, we will apply a set of novel biomarkers in AA that provide a translational platform to monitor novel treatments for AA, and may provide insight for other autoimmune diseases.**

METHODS

Specific Aim 1: To evaluate the efficacy of treating 68 patients with mild to moderate patch type alopecia areata for six months with intralesional triamcinolone acetonide (IL TAC) at a strength of 2.5mg/ml versus treatment with intralesional triamcinolone acetonide 5mg/ml versus treatment with intralesional triamcinolone acetonide 10mg/ml versus intralesional saline placebo and to monitor the duration of therapy for 6 months following treatment.

The primary efficacy endpoint of this intention to treat trial will be the proportion of responders in the treated groups compared to the control group after 6 months of treatment, with responders being defined as subjects achieving 50% or greater hair re-growth from baseline as assessed by SALT score at week 24. This is a relatively strict definition for defining responders and non-responders and was chosen to minimize responses in the “vehicle” arm,

[figure not shown]

Figure 1

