in which fewer than 10% are expected to achieve this magnitude of hair regrowth spontaneously. In contrast, clinical experience would suggest that approximately 50% of subjects treated with either dose of IL TAC may achieve $\geq 50\%$ improvement in SALT score after 6 months of treatment. The goal of this study is to validate or refute this clinical impression and to objectively and precisely quantify the treatment effect of 2.5mg/ml, 5mg/ml or 10mg/ml of IL TAC in AA.

Subjects will be randomized 1:1:1:1 to the placebo or treatment arms, and will receive 6 months of treatment with the study medication or placebo. IL TAC 2.5mg/ml, 5mg/ml, 10mg/ml or placebo will be administered at baseline, then every 4 weeks thereafter for 5 cycles (weeks 4, 8, 12, 16, 20) for a total treatment period of 6 months. Percent hair regrowth from baseline will be determined by SALT measurements following 4, 8, 12, 20 and 24 weeks of treatment. Punch biopsies and peripheral blood will be obtained at baseline prior to treatment, and then once again at a time point between weeks 4 and 20, to be determined by the investigator as indicated by clinical considerations such as variation in the timeline to regrowth from one subject to another, for immunomonitoring/biomarker studies. Additional, optional scalp biopsies and blood draws may be taken at other key time points in order to monitor response to therapy at the discretion of the investigator and with the consent of the study subject. Efficacy will be measured by change in hair re-growth as determined by physical exam and photography, as well as by patient and physician global evaluation scores. Physician and patient global evaluation scores will be determined based on the use of similar 100mm Visual Analogue scales with 0 labeled as no scalp hair loss and 100 labeled as complete scalp hair loss. Patients and physicians will place a vertical mark along the horizontal line depending on their assessment of the degree of hair loss present at the time of assessment.

As secondary endpoints, efficacy will be measured by changes in hair re-growth as a continuous variable as determined by physical exam, SALT score and Canfield photography, as well as patient and physician global evaluation scores.

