Power analysis is based on a chi-squared test of proportions of responders in the 4 study groups, where response is defined as 50% reduction in SALT score. Effect size is quantified in terms of Cohen's w , a function of the response rates in the fourgroups (15). A minimal treatment effect size of 40% (Cohen's $w = 0.4$) i.e. a 50% response rate for active drug (IL TAC 2.5mg/ml, 5mg/ml or 10mg/ml) versus a presumed spontaneous remission response rate of 10% for patients receiving inactive IL saline, would be considered clinically meaningful in this study. To achieve 80% power to detect the desired effect size of 40% with a usual 5% level of significance (alpha), we would require approximately 17 subjects per arm (68 subjects in total). With this sample size, an effect size of 50% (Cohen's $w = 0.5$, "large" effect) would ensure approximately 95% power. Our postulated effect size for IL TAC is based on impressions due to clinical use of IL TAC in AA, however an explicit aim of this pilot study is to objectively and more precisely quantify the actual treatment effect of the various doses of IL TAC versus saline placebo.

Data Analysis Plan

The primary analysis will be a comparison of response rates in the 4 study groups, using a chi-squared test of proportions. If the 4-group comparison is significant, we will compare the efficacy and safety profiles of the three doses of intralesional triamcinolone head to head. For secondary outcomes that are binary (response/non-response), we will follow the same strategy. For secondary outcomes that are continuous (e.g. change in SALT measurement or PGA), we will conduct 4-group ANOVA tests, followed by pairwise

comparisons, if necessary. In both cases, Bonferroni correction will be made to adjust for multiple testing. To assess safety, we will summarize and test the incidence rates of adverse events across groups.

If possible, we will attempt to stratify the patients based on baseline degree of hair loss e.g. 0-25% vs. 26-50% hair loss in order to assess if response is correlated with degree of hair loss present at baseline. (Olsen E. Investigative guidelines for alopecia areata.

Dermatologic therapy 24, 2011 311-319

All outcomes will be analyzed on the intent to treat (ITT) basis.

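### The written follow-up to the 4-group test compares only the active doses with each other; no dose-versus-saline contrast, risk difference or interval is specified

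*Combined protocol and SAP*

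**What the plan says.** All references are to the combined protocol and SAP.

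- **Primary test** (Data Analysis Plan): "The primary analysis will be a comparison of response rates in the 4 study groups, using a chi-squared test of proportions".
- **Follow-up** (same section): "If the 4-group comparison is significant, we will compare the efficacy and safety profiles of the three doses of intralesional triamcinolone head to head".
- **Binary secondary outcomes**: "For secondary outcomes that are binary (response/non-response), we will follow the same strategy".
- **Continuous secondary outcomes**: "we will conduct 4-group ANOVA tests, followed by pairwise" comparisons if needed, with the pairs not named.
- **Multiplicity**: "In both cases, Bonferroni correction will be made to adjust for multiple testing". The number of comparisons is not given.
- **Endpoint wording** comes in two forms. METHODS, Specific Aim 1 has "the proportion of responders in the treated groups compared to the control group after 6 months of treatment", and Assessment of efficacy repeats this almost unchanged. The primary efficacy outcome under Study outcomes instead compares responder proportions across each group.
- **Estimation aims**: METHODS, Specific Aim 1 sets the goal to "objectively and precisely quantify the treatment effect of 2.5mg/ml, 5mg/ml or 10mg/ml of IL TAC in AA". The Sample size section makes it an explicit aim to "quantify the actual treatment effect of the various doses of IL TAC versus saline placebo".

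No section attaches a test, effect measure or interval to the comparison with saline. The interim analysis text does not supply one either.

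**The concern.** A significant 4-group test says that the four response rates are not all equal. It does not say which differ. The step that should locate the difference is written for the three active strengths only, so a team following the text would report an overall p-value and then how the doses compare among themselves. The comparison that the treated-versus-control endpoint and the estimation aims call for would have to be improvised.

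Four choices are left open until the data are in hand: pooled active or each dose, the effect measure, the interval method, and the Bonferroni divisor. At stake is whether a statement that a given strength beats saline, and by how much, can be presented as planned in advance.

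**Working it through.** **Inputs.** From Sample size: 17 per arm (68 in total), alpha 0.05, 10% response on saline and 50% on active drug, Cohen's w = 0.4 for 80% power and w = 0.5 for about 95%. Assumed here because the plan is silent: two-sided pairwise tests, a divisor of 3 (0.05/3 = 0.0167), and all 68 patients with a week-24 result.

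**Step 1. The plan's own figure.** For the 3-df chi-squared test the noncentrality is N × w².
- w = 0.4: 68 × 0.16 = 10.88, power 79.9%.
- w = 0.5: 68 × 0.25 = 17, power 94.8%.

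Both stated figures reproduce, but they describe the 4-group test only. (Separately, rates of 10/50/50/50 correspond to w = √(0.03/0.24) = 0.354 rather than 0.4. The steps below therefore use the rates directly.)

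**Step 2. Method.** Each arm has 0 to 17 responders, giving 18⁴ = 104,976 possible outcomes. Each is weighted by its binomial probability. The 4-group statistic is Σ 17(pᵢ − p̄)² / [p̄(1 − p̄)], tested at 0.05 on 3 df. Pairwise tests are Fisher or uncorrected Pearson at 0.0167.

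**Step 3. Results** (rates as saline / three doses). The 10/10/10/50 case is an assumption, to show a trial in which one dose works.

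| | 10/50/50/50 | 10/10/10/50 |
|---|---|---|
| 4-group test significant | 75.9% | 84.5% |
| Given that: any dose-versus-dose difference, Fisher / Pearson | 3.3% / 8.3% | 64% / 90% |
| Given that: at least one dose above saline, Fisher / Pearson | 93.2% / 99.8% | 49% / 73% |

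At 10/50/50/50, saline has the strictly lowest observed rate in 99.3% of significant trials.

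**Step 4. What a named contrast can deliver.** For one dose against saline, 50% versus 10% with 17 per arm at 0.05/3, power is 41.5% (Fisher) or 62.6% (Pearson). Counting only trials where the 4-group test is also significant, at 10/50/50/50:
- at least one dose succeeds in 71% (Fisher) or 76% (Pearson);
- all three succeed in 15% (Fisher) or 38% (Pearson).

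**Step 5. Precision.** The expected half-width of the 95% Newcombe interval for 50% versus 10% is 26 points. As an example, 9/17 versus 2/17 is a difference of 7/17 = 41 points, with interval 10 to 64. Fisher gives p = 0.0255, above 0.0167; Pearson gives p = 0.010, below it. An unadjusted interval and an adjusted test can therefore disagree.

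**The case against.** **The intent is clear, and the 4-group test fits one version of the endpoint.** Both are true. The comparator, time point and overall test are fixed, and the wording under Study outcomes, which compares proportions across each group, is what a 4-group test addresses. A reader might infer that the plan forgets placebo or that its primary test misses the trial's question. The documents do not support that. The mismatch is with the treated-versus-control wording and the estimation aims.

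**The low dose-versus-dose rate is no defect.** Correct. At 10/50/50/50 the doses are equal, so finding a difference in only 3% to 8% is proper behaviour. If one dose works, the written step detects a difference more often than the saline contrasts do (64% to 90% against 49% to 73%). This stands, but a difference between two strengths still does not show that either beats saline.

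**Anyone can subtract the rates.** True, and with saline lowest in 99% of significant trials the direction would seldom be in doubt. That limits the harm. It does not make the contrast, interval or divisor prespecified.

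**Bonferroni implies all pairs.** For continuous outcomes, pairwise comparisons after a 4-group ANOVA would naturally include saline. For binary outcomes the named follow-up covers active doses only, so assuming three or six comparisons would be a guess.

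**It is a pilot.** That argues for estimates with intervals more than against them.

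**Conclusion.** The point holds as a gap between the stated aims and the written analysis, and should be fixed. The follow-up for the primary outcome, and by reference for binary secondary outcomes, leaves out the dose-versus-saline comparison, and no effect measure or interval is specified for it.

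The effect on testing is small at the planned rates. A reader might infer that a significant result would mislead; the 93% to 99.8% and 99% figures show otherwise. What is lost is a contrast and an estimate fixed in advance. Naming the contrasts would also reveal, without curing, modest per-dose power of about 41% to 63%.

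The plan's rates and arm size are its own. The divisor of 3, two-sided tests, complete week-24 data and the one-effective-dose scenario are assumptions of this check. With a divisor of 6, per-dose Fisher power falls to 36%.

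**What to change.** 1. Keep the 4-group chi-squared test as the primary test.
2. Extend the follow-up sentence: if that test is significant, the three week-24 dose-versus-saline comparisons are the main contrasts, followed by the three dose-versus-dose comparisons.
3. State the number of comparisons in the Bonferroni correction and the pairwise test. Both are the trial statistician's choice, made in advance. For orientation, six contrasts at 0.05/3 after the 4-group test have a family-wise error of at most 4.1% with Fisher but up to 6.3% with Pearson, over the rate patterns examined; Fisher pays for this in power.
4. Whatever the 4-group test shows, report the week-24 risk difference with 95% confidence interval for each dose versus saline, labelled unadjusted.
5. Apply the same contrasts to binary and continuous secondary outcomes only up to week 24. Do not extend them to weeks 36 and 48, because non-responders may leave or receive open-label drug after week 24. Do not extend them to relapse, which is assessed only in responders (17 × 0.10 = 1.7 expected on saline) and has its own planned tests.

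The cost is a few lines of text, with no added patients, visits or data. The plan should state the downsides openly: per-dose power of about 41% (Fisher) to 63% (Pearson) at 0.05/3, and intervals of about ±26 points.

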- Patients will have up to 50% total scalp hair loss at baseline as measured by the Severity of Alopecia Tool (SALT) (2) score.
- Duration of hair loss greater than 3 months without an upper limit of duration as long as there is reason to believe that regrowth is possible in the opinion of the investigator.
- No evidence of active, ongoing regrowth present at baseline.
- Patients with alopecia totalis/universalis can be included as long as the current episode of hair loss meets the criteria of up to 50% total hair loss (i.e. they may have had a

previous episode of AT or AU which demonstrated regrowth of hair, and they are not currently AT or AU), and as long

- Patients with more than 50% total scalp hair loss at baseline can be included as long as the specified area to be treated is limited to less than 50% of total scalp area

Exclusion criteria

- Patients with a history of or existing skin diseases affecting the scalp such as psoriasis or seborrheic dermatitis and patients with evidence of infection or skin cancer in the treated areas
- Patients in whom the diagnosis of alopecia areata is questionable
- Patients in whom regrowth is present/evident at baseline in the areas to be treated
- Patients with active medical conditions or malignancies (except adequately treated basal or squamous cell carcinoma of the skin) which in the opinion of the investigator would increase the risks associated with study participation, including patients with a history of recurrent infections
- Women of childbearing potential who are unable or unwilling to use two forms of birth control for the study duration or women who are pregnant or nursing
- Patients known to be HIV or hepatitis B or C positive or otherwise immunocompromised
- Patients with evidence of adrenal cortex abnormality or previous significant adverse reaction to intralesional steroids
- Patients unwilling or unable to discontinue treatments known to affect hair regrowth in alopecia areata
- Patients who have been treated with intralesional steroids, systemic steroids, anthralin, squaric acid, DPCP (diphenylcycloprophenone), protopic, minoxidil or other medication which in the opinion of the investigator may affect hair regrowth, within one month of the baseline visit.

Study procedures

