Screening: A complete medical history will be taken. Patients will be specifically asked about renal, hepatic or adrenal abnormalities and pregnancy (women of child bearing potential only). In keeping with current standard of care, no routine blood work will be done, unless it is deemed necessary by the investigator. Patients will be randomly assigned to IL TAC 2.5mg/ml, IL TAC 5mg/ml or IL TAC 10mg/ml or intralesional saline in a 1:1:1:1 ratio based on a computer generated randomization list. The list will be generated prior to study initiation. Based on the randomization list, patients will be assigned to treatment vs. placebo based on the order in which they are enrolled. The assignment will be made by study personnel not involved in making clinical assessments or evaluations. The patient and the assessing physicians will remain blinded to the treatment assignment for the duration of the study. Baseline assessments of disease severity will be done, including SALT, Physician global assessment (PGA), patient global assessment and patient quality of life assessment. Patients will have study medication injected once per month by the study physician in accordance with current standard of care clinical practice. Per current clinical practice, attempts will be made to treat all areas of hair loss due to AA, however (also in accordance with current standard of care in clinical practice) the dose of intralesional triamcinolone injected will be limited to a maximum of 30mg per month(16, 4). Therefore, patients being

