S: Scalp hair loss

  S0 = No hair loss	  S4 = 76%-99% hair loss
  S1 = less than or equal to 25% hair loss	  a = 76%-95% hair loss
  S2 = 26%-50% hair loss	  b = 96%-99% hair loss
  S3 = 51%-75% hair loss	  S5 = 100% hair loss

Olsen/Canfield

FIG. 2. Olsen/Canfield tool for determination of %scalp hair loss. Percentages represent scalp surface area (reprinted with permission).

[figure not shown]

Figure 9. SALT score.

The percentage of hair loss in any one of the four views (areas) of the scalp = the percentage hair loss x percent surface area of the scalp in that area. The SALT score then equals the sum of the scalp hair loss in each area.

- (a) Top (left side view) = $95\% \times .18 = 17.1$
- (b) Second (right side view) = $90\% \times .18 = 16.2$
- (c) Third (top of scalp) = $95\% \times .40 = 38$ (realizing that most of hair loss is probably male pattern hair loss)
- (d) Bottom (back of scalp) = $55\% \times .24 = 13.2$

$a+b+c+d = 17.1 + 38 + 16.2 + 13.2 = 84.5\% \text{ hair loss or SALT } 84.5$

Body hair loss

B0 = No body hair loss

B1 = some body hair loss

B2 = total (100%) body hair loss

Nail involvement

N0 = No nail involvement

N1 = some nail dystrophy

N1a = 20 nail dystrophy

Percentage change from baseline (% regrowth) =

$[(SALT \text{ BL} - SALT \text{ F/U}) / SALT \text{ BL}] \times 100\% = \% \text{ change from baseline}$

Absolute regrowth = SALT BL – SALT F/U = absolute change from BL

Study outcomes

Primary efficacy outcome:

1. Comparison of the proportion of responders in each group, with response defined as 50% change (% change NOT absolute change) in SALT score from baseline (50% regrowth at week 24).

This is a relatively strict definition for defining responders and non-responders and was chosen based on consensus of clinicians and AA experts that 50% reduction in SALT score represents clinically meaningful response and to minimize responses in the “vehicle” arm, in which fewer than 10% are expected to achieve this magnitude of hair regrowth spontaneously. This outcome was also used in two recent RCT trials (Strober et al. 2009 and Price et al. 2008) evaluating therapies for AA.

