As secondary endpoints, efficacy will be measured by changes in hair re-growth as a continuous variable as determined by physical exam and Canfield photography, as well as patient and physician global evaluation scores. To assess the durability of responses, patients who achieve 50% reduction in baseline SALT score will continue to be followed for an additional 6 months off treatment.

Secondary efficacy outcomes will include:

1. Percent hair regrowth from baseline determined by SALT measurements following 12, 24 weeks of treatment and at weeks 36 and 48 following discontinuation of treatment (Price et al Efalizumab study)
2. Comparison of the proportion of responders in each group, with response defined as 50% change in SALT score (50% regrowth) from baseline, at weeks 12, 36 and 48.
3. Comparison of the proportion of subjects in each group attaining global overall improvement SALT score of A5 (100% coverage) supported by </= SALT 25 at weeks 12, 24, 36 and 48.
4. Change in PGA (Physician global assessment) based on evaluation of live evaluations and standardized photographs between baseline, week 12, 24, 36 and 48
5. Change in patient global assessment (100mm Visual analogue scale) between baseline, Week 12, 24, 36 and 48
6. Change in patient quality of life assessment (DLQI or DQLS) from baseline to weeks 12, 24, 36 and 48. (Finlay and Khan 1994).
7. Frequency of occurrence and timing of relapse (as defined above) in responders followed for 6 months off therapy.

Safety and tolerability measures:

Incidence and severity of adverse effects (AEs) including the presence and degree of skin atrophy.

Incidence of treatment-emergent laboratory abnormalities.

Sample size

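### Continuous secondary outcomes are analysed by unadjusted ANOVA on change although every baseline is collected; ANCOVA on the same measure's baseline is usually more precise at almost no cost

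*Combined protocol and SAP*

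**What the plan says.** The Data Analysis Plan says: "For secondary outcomes that are continuous (e.g. change in SALT measurement or PGA), we will conduct 4-group ANOVA tests". Pairwise comparisons follow if needed, with Bonferroni correction. No covariate is named there or elsewhere.

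The numbered secondary outcomes under Study outcomes include three change scores:

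- Item 4: "Change in PGA (Physician global assessment) based on evaluation of live evaluations and standardized photographs between baseline, week 12, 24, 36 and 48".
- Item 5: "Change in patient global assessment (100mm Visual analogue scale) between baseline, Week 12, 24, 36 and 48".
- Item 6: "Change in patient quality of life assessment (DLQI or DQLS) from baseline to weeks 12, 24, 36 and 48".

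The SALT section also defines an absolute change, "Absolute regrowth = SALT BL – SALT F/U = absolute change from BL", but this is not in the numbered list. The listed continuous SALT outcome is item 1, a percentage: "Percent hair regrowth from baseline determined by SALT measurements following 12, 24 weeks of treatment and at weeks 36 and 48". The Data Analysis Plan's example of SALT change does not say which of the two is meant.

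The baselines are available. Study procedures, Screening, says: "Baseline assessments of disease severity will be done, including SALT, Physician global assessment (PGA), patient global assessment and patient quality of life assessment". The Day 0 list and the Schedule of Assessments agree.

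The analysis plan uses baseline in one other way. If feasible, patients are to be stratified by SALT category (0–25% against 26–50%) to see whether response is related to severity. That is conditional, concerns SALT only, and does not adjust the ANOVA of the other measures.

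**The concern.** An ANOVA on change assumes that each unit of baseline carries over fully into follow-up. For visual analogue ratings and quality-of-life scores the slope is usually below 1, because of measurement error and regression to the mean. The change score then over-corrects. Its variance is larger than it need be, and an arm that starts worse by chance tends to show more improvement.

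The protocol says that a purpose of this pilot is to quantify the treatment effect more precisely. With 17 per arm and a Bonferroni-corrected pairwise step, intervals for the difference from saline on PGA, patient global and quality of life will be wide. Values already in the database could narrow them. Naming the covariate in advance also removes a later choice between adjusted and unadjusted results if baselines look unequal.

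**Working it through.** **Inputs from the documents.** 17 per arm, 68 in total, 1:1:1:1 allocation, alpha 0.05 (Sample size; Methods). No SD or baseline–follow-up correlation is given for any continuous outcome, so correlation rho (0.3 to 0.9) and the follow-up/baseline SD ratio k are assumptions.

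**The plan's own figure.** The only stated power is for the primary four-group chi-squared test. With 3 df and noncentrality 68 × 0.4² = 10.88, power is 79.9%; at w = 0.5 (noncentrality 17.0) it is 94.8%. Both match the stated 80% and 95%. No figure is stated for the continuous outcomes.

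**Variance comparison.** With baseline SD s0 and follow-up SD s1:

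- Change score: s0² + s1² − 2·rho·s0·s1
- ANCOVA residual: s1²(1 − rho²)
- Difference: (s0 − rho·s1)², which is never negative

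With equal SDs the ratio is (1 + rho)/2. Estimating one slope takes the error df from 64 to 63 and multiplies the contrast variance by 1 + 1/(68 − 4 − 2) = 1 + 1/62 = 1.016. The power column uses the noncentral F with three equal active arms against saline, at the effect where ANOVA on change has 80%.

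| rho | Variance ratio, cost included | Equivalent N for ANOVA (68/ratio) | ANCOVA power |
|---|---|---|---|
| 0.3 | 0.660 | 103 | 94% |
| 0.5 | 0.762 | 89 | 90% |
| 0.7 | 0.864 | 79 | 86% |
| 0.9 | 0.965 | 70 | 81.5% |

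Simulation (8,000 trials per setting) gave ratios of 0.67, 0.75, 0.87 and 0.96, with type I error between 4.4% and 5.3% for both methods.

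**Unequal SDs.** The ratio is k²(1 − rho²)/(1 + k² − 2·rho·k) × 1.016. For rho from 0 to 0.95 it runs over 0.37–0.57 at k = 0.75, 0.62–1.016 at k = 1.25 and 0.56–1.014 at k = 1.5. The worst case is 1.016, reached when the slope rho·k is 1; power then falls from 80% to about 79.3%. With equal SDs, break-even is at rho of about 0.97.

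**Interval width at rho 0.5, equal SDs.** The change-score SD is 1, so the standard error of an arm difference is √(2/17) = 0.343 SD; for ANCOVA it is 0.343 × √0.762 = 0.299.

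- 95% half-width: 2.00 × 0.343 = 0.69 SD, against 2.00 × 0.299 = 0.60 SD.
- Bonferroni over six pairs (alpha 0.05/6): 2.72 × 0.343 = 0.93 SD, against 2.72 × 0.299, about 0.82 SD.

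**Chance imbalance.** A baseline difference between two arms has SD 0.34. The probability that at least one of three active arms starts more than 0.5 SD from saline is 33%. With equal SDs, a 0.5 SD gap moves the unadjusted change difference by (1 − rho) × 0.5, which is 0.25 SD at rho 0.5.

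**Percent SALT regrowth is different.** It already divides by baseline. In an assumed model (baseline uniform 2–50; mean regrowth 10% on saline and 40% on active; regrowth SD 30, 35 or 45 percentage points; no rating noise), ANOVA on percent regrowth had 85%, 71% and 48% power. ANCOVA of follow-up SALT had 72%, 57% and 37%. The order reverses only with added SALT noise, for which the documents give no figure. Percent change is, however, unstable at small baselines, and the inclusion criteria set no lower limit on SALT: a 2-point difference is 2/5 = 40 percentage points at baseline 5 and 2/50 = 4 at baseline 50.

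**The case against.** The strongest reply is that nothing here is an error. The trial is called a pilot, only the binary endpoint is powered, no precision target is set for these outcomes, and the planned test is valid. That stands, and it limits the point to a suggested improvement.

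The second reply is about size. The equal-SD figures may flatter ANCOVA if regrowth is proportional to baseline. In the proportional model above, now comparing ANCOVA with absolute change, the variance of an active–saline difference falls by only about 11%, 8% and 5% at regrowth SDs of 30, 35 and 45 points. Omnibus power rises from 64% to 73%, 51% to 57% and 35% to 39%. With no treatment effect and no noise, the gain is about nil. Rating noise, which visual analogue scales have, increases the benefit: at noise SD 8 and regrowth SD 30, power rose from 29% to 39%. In every setting with a treatment effect ANCOVA was the better method. The gain is therefore real, but may be well below a quarter.

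Other points stand as conditions:

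- Under proportional regrowth the slopes differ by arm, so a common-slope ANCOVA estimates an average difference.
- Measures are taken at both screening and Day 0, so the baseline visit must be named.
- The quality-of-life instrument is left open between two scales.
- Open-label drug after the 3-month interim analysis would dilute week-24 contrasts under either method.

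Apart from the slope question, these affect the planned ANOVA equally.

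**Conclusion.** The concern holds as a low-cost improvement to consider. The plan analyses change in PGA, patient global and quality of life without adjustment, although each baseline is collected. ANCOVA lowers the variance of arm differences by anything from nothing to about a third with equal SDs and rho of 0.3 or more, and costs at most about 1.6% of variance plus one error degree of freedom. No single figure can be given, because it depends on correlations and SDs that the documents do not supply.

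The primary chi-squared test and the sample size of 68 are unaffected, and no superiority over percent SALT regrowth is claimed. The benefit is clearest at weeks 12 and 24. Afterwards nonresponders need not be followed or may take open-label drug, and baseline adjustment does not repair that.

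**What to change.** In the Data Analysis Plan, state that PGA, patient global, quality of life and any analysis of absolute SALT change at weeks 12 and 24 will use ANCOVA with treatment group and the baseline value of the same measure. Say which pre-treatment visit supplies the baseline, and use the same quality-of-life instrument at baseline and follow-up. Keep the Bonferroni pairwise step, and report adjusted differences from saline with confidence intervals. A treatment-by-baseline check can be added as a sensitivity analysis.

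Keep percent SALT regrowth as the listed secondary outcome. An ANCOVA of follow-up SALT on baseline SALT can sit beside it as a supporting analysis, given the instability of percentages at small baselines.

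The cost is wording in the plan and one residual degree of freedom (64 to 63). No extra subjects, visits or measurements are needed.
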